10.4.2.2 Descriptive Statistics

Descriptive statistics will be used to summarize the DLT for both hematologic and non-hematologic toxicity per type and grade. The same summary statistics will be used for the response rate and clinical benefit rate. Response rate is defined as the proportion of subjects with complete response or partial response. Clinical benefit rate is defined as the proportion of subjects with complete response or partial response or stable disease. Kaplan-Meier product limit survival plots will be generated and median survival time and associated 95% CI will be estimated for each arm.

Descriptive statistics will be used to summarize the AEs and SAEs for both hematologic and non-hematologic toxicity per type and grade. Safety follow-up: Approximately 30 days after the last dose of both study drugs or before initiation of a new antitumor treatment, whichever occurs first.

10.5 Data Analysis Plan

10.5.1 Toxicity

The study populations will include the following:

- The Safety Population, which will include all patients who received at least 1 dose of enzalutamide;
- The Response Population, which will include all patients who received enzalutamide.

10.5.2 Response & Progression Free Survival (PFS)

10.5.2.1 Tumor Response

Tumor response will be assessed using RECIST 1.1.

10.5.2.2 Overall Response, Target Lesion Response, Non-Target Lesion Response:

Overall Response: If measurable disease, then confirmed by repeat assessments 4 or more weeks after initial documentation of the response.

If evaluable but not measurable, response will be assessed either quantitatively, in the case of patients with elevated tumor markers, or descriptively (e.g., resolution of bone scan findings, decrease in tumor related pain symptoms).

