4.1 Inclusion Criteria

1. ER+ Her2- breast cancer
2. Metastatic
3. Female, at least 18 years of age
4. Candidate for fulvestrant therapy – patients who have started fulvestrant may enter this trial if within 3 months of starting fulvestrant
5. Measurable or evaluable by RECIST 1.1

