6.1 Study Procedures

Study Phase	Screening	Treatment				Progression	Follow-up
		1	5	9	13 [1]		
Study Week	-4 to -1	1	5	9	13 [1]	varies	varies [10]
Window (Days)	28	n/a	+/- 7	+/- 7	+/- 7	n/a	+/- 7 days
Informed Consent	x						
Eligibility	x						
Medical History	x						
Archived Tissue Collection [2]	x						
Tumor Imaging [3]	x			x			
Physical Exam	x	x	x	x	x	x	
Adverse Events	x	x	x	x	x	x	x
Concomitant Medications	x	x	x	x	x	x	
Study Drug Dispensing [4]		x		x			
Fulvestrant [9]		x	x	x	x		
Tumor Biopsy		x [5]	x			optional	
Hematology, Serum Chemistry [6]	x	x [8]	x	x	x	x	
PT/INR, PTT [11]	x		x			x	
Urine Pregnancy Test [12]	x						
Circulating Tumor Biomarkers	x	x [8]	x	x	x	x	
CTCs [7]	x	x [8]	x	x		x	
Survival & Recurrence Follow-up							x

[1] Continue every 4 weeks until progression.

[2] From primary lesion and/or metastatic sites previously biopsied. If tissue is available, archival blocks from both sites (primary and metastatic) should be collected, however, the top priority is the primary tissue.

[3] Within approximately 28 days before study entry and includes CT with contrast (unless medically contraindicated) of chest, abdomen, and pelvis. Bone assessments as clinically indicated. Thereafter, perform assessments every 8 weeks up to week 49 and then every 12 weeks thereafter until progression is documented per RECIST 1.1 or permanent treatment discontinuation. MRI is acceptable if CT not possible. Use the same testing across time.

[4] Refill every 8 weeks as long as patient remains on active treatment.

[5] Before treatment, but after eligibility determined.

[6] Hematology: hematocrit, hemoglobin, platelet count, red blood cell count, total neutrophils (absolute), white blood cell count with differential. Chemistry: albumin, alkaline phosphatase, ALT (alanine aminotransferase), AST (aspartate transaminase), blood urea nitrogen and creatinine; Ca⁺⁺, Cl⁻, K⁺, Na⁺; glucose (non-fasting), total bilirubin, total CO₂ (bicarbonate), total protein.

[7] CTCs will be collected at all participating sites, coded to remove patient identifiers, and shipped to UCCC and USC for processing as outlined in the lab manual.

[8] Only one sample is needed pretreatment (either during screening or prior to treatment on C1D1).

[9] Given IM on days 1, 15, and 28 (C2D1), and then every 4 weeks as per standard of care (SOC).

[10] 30 days after the last dose of enzalutamide or before initiation of a new antitumor treatment, whichever occurs first. May be done by telephone.

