6.3 Laboratory Procedures/Evaluations

6.3.1 Blood

Routine blood tests (chemistries, hematology) will be obtained every month as clinically indicated. Tumor markers to be followed every 1-2 months as clinically indicated.

Blood for potential pharmacogenomics testing will be obtained at baseline. The white cell pellet required for this sample will be obtained from the baseline plasma vacutainer.

Plasma for tumor related exosomes and other circulating tumor products will be obtained each cycle on day 1 (10 ml).

Blood for circulating tumor cells will be obtained day 1 of cycles 1, 2, and 3 (up to 30ml each time).

Baseline:

- 1 plasma vacutainer (green top, lithium heparin, 10ml)
- 1 serum vacutainer (red top, 10ml)
- 2-3 tubes for CTC sample collection (up to 30ml)

~Week 5:

- 1 plasma vacutainer (green top, lithium heparin, 10ml)
- 2-3 tubes for CTC sample collection (up to 30ml)

~Week 9:

- 1 plasma vacutainer (green top, lithium heparin, 10ml)
- 2-3 tubes for CTC sample collection (up to 30ml)

~Week 13:

- 1 plasma vacutainer (green top, lithium heparin, 10ml)

End of study:

- 1 plasma vacutainer (green top, lithium heparin, 10ml)
- 2-3 tubes for CTC sample collection (up to 30ml)

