10.2 Sample Size

10.2.1 Determination of Sample Size

The primary outcome is the clinical benefit rate. Assuming the undesirable rate of 10% and desirable rate of 30%, a sample size of 24 provides 89% power to detect this 25% rate difference using an exact binomial test with a one-sided alpha of 0.085. If 5 or more patients show clinical benefit the drug combination warrants further evaluation. During treatment period, patients might withdraw due to toxicity or loss to follow-up before on treatment for 24 weeks. Table below summarize the statistical power and the decision rule for sample size from 24 to 20, a 20% loss in the total sample size, which is the upper bound for loss seen in practice.

Statistical Power	n	Actual Alpha	Reject H0 If R ≥
0.89	24	0.085	5
0.86	23	0.073	5
0.84	22	0.062	5
0.80	21	0.052	5
0.76	20	0.043	5

R is the response as the clinical benefit

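### Patients without measurable disease may be assessed for response on tumour markers or pain, without confirmation, although the plan says response follows RECIST 1.1

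*Combined protocol and SAP*

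**What the plan says.** Section 10.5.2.1 states: "Tumor response will be assessed using RECIST 1.1". Section 10.5.2.2 follows with two rules.

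- **Measurable disease:** "If measurable disease, then confirmed by repeat assessments 4 or more weeks after initial documentation of the response".
- **Evaluable but not measurable disease:** response is judged quantitatively where tumour markers are elevated, or "descriptively (e.g., resolution of bone scan findings, decrease in tumor related pain symptoms". No marker, size of fall, pain scale, time point or confirmation is given.

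Other sections determine how far this reaches.

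- Section 4.1 admits patients who are "Measurable or evaluable by RECIST 1.1", with no cap on the non-measurable group.
- Section 10.4 gives disease evaluation to the investigators and leaves the RECIST version blank. Section 3.1 describes a single-arm, open-label trial.
- Section 6.1, footnote [3], schedules CT of chest, abdomen and pelvis every 8 weeks to week 49, but "Bone assessments as clinically indicated". Section 6.3.1 has "Tumor markers to be followed every 1-2 months as clinically indicated". The section 6.1 schedule contains no pain assessment.
- Section 2.2 defines clinical benefit as complete and partial response plus stable disease, with the 24-week duration next to stable disease. Sections 10.4.2.1 and 10.4.2.2 repeat the definition with no duration. The synopsis names the primary endpoint as clinical benefit rate at 24 weeks, and the synopsis and section 2.3 place the response rate at 24 weeks.

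**The concern.** The two parts of section 10.5.2 cannot both be followed for a patient with non-measurable disease. Tumour markers without a threshold and reduced pain are not lesion-based assessments, and they are the least reproducible inputs in the plan. Both patient and investigator know the treatment, and pain can change for reasons other than tumour shrinkage. These inputs are also the ones with no confirmation rule and no fixed collection schedule.

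The response rate takes any such call directly: with 24 patients, each one adds 1/24, or 4.2 percentage points. The clinical benefit rate is less exposed. A non-measurable patient who is progression-free at 24 weeks would presumably count as stable disease anyway, so the rate is inflated only by patients credited with a response who do not get that far. The go threshold is only 5 patients, so few miscounts are needed to matter. The same response label also enters the exploratory split into responders and non-responders (sections 1.3.1 and 10.2.2).

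**Working it through.** **Inputs from section 10.2.1.** n = 24; "Assuming the undesirable rate of 10% and desirable rate of 30" per cent; exact one-sided binomial test; go if 5 or more patients benefit; stated alpha 0.085 and power 0.89. The same sentence speaks of "power to detect this 25% rate difference", but 30% − 10% = 20 points. The table matches 30%, so the 25% is a wording slip and plays no part here.

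**Step 1: reproduce the plan's figures.** With X ~ Binomial(24, p):

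- P(X ≥ 5 | p = 0.10) = 1 − Σ(x = 0 to 4) C(24, x) 0.10^x 0.90^(24−x) = 0.0851
- P(X ≥ 5 | p = 0.30) = 0.889

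Both agree with the plan, and the rows for n = 20 to 23 reproduce as well. The sample-size calculation is sound; the question is what counts as a success.

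**Step 2: exactly one or two miscounted patients.** Suppose k patients without true benefit are counted as successes and the others benefit independently at 10%.

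- k = 1: 4 or more of the other 23 are needed; P(Binomial(23, 0.10) ≥ 4) = 0.193
- k = 2: 3 or more of the other 22 are needed; P(Binomial(22, 0.10) ≥ 3) = 0.380

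**Step 3: miscalls as a rate.** Let f of the 24 patients be non-measurable, and let q be the chance that such a patient without true benefit is scored as a success. The documents give neither, so both are assumptions. A measurable patient succeeds with probability 0.10, and a non-measurable patient with probability 0.10 + 0.90q. The total is Binomial(24 − f, 0.10) + Binomial(f, 0.10 + 0.90q).

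| f | q | 0.10 + 0.90q | P(5 or more of 24) |
|---|---|---|---|
| 0 | – | – | 0.085 |
| 2 | 5% | 0.145 | 0.096 |
| 4 | 10% | 0.190 | 0.133 |
| 8 | 10% | 0.190 | 0.192 |
| 10 | 20% | 0.280 | 0.414 |

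**Step 4: which reading the table needs.** Steps 2 and 3 apply only if a response can count as clinical benefit without 24 weeks free of progression. Sections 2.2, 10.4.2.1 and 10.4.2.2 allow that. If the synopsis wording governs, a patient who progresses before week 24 is not a success, and this route adds little or nothing to the primary rate. The effect on the response rate is narrower on that reading too, but it remains: a non-measurable patient who is merely stable at 24 weeks can still be called a responder on markers or pain.

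**The case against.** Several points on the other side have weight.

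- **Timing.** A reader might infer that a bone-only patient with less pain at week 5 is already a primary-endpoint success whatever happens later. The documents do not establish this. The synopsis puts the clinical benefit rate at 24 weeks, and the synopsis and section 2.3 do the same for the response rate. The definitions conflict, so the early-pain success is permitted by some sections and not by others.
- **Category.** Section 10.5.2.2 says response is assessed descriptively; it does not say that reduced pain is recorded as a partial response. This stands, but it leaves the coding to the investigator, which is the problem.
- **Imaging.** It would be wrong to say that such a patient has no image of her bones. The 8-weekly CT covers chest, abdomen and pelvis and continues until RECIST 1.1 progression or permanent discontinuation of treatment. Only dedicated bone assessment is left to clinical indication. Resolution of bone scan findings is itself an imaging result, so the objection is to markers and pain. With progression tied to RECIST 1.1, PFS is also less affected.
- **Size.** The need for tumour accessible to two fresh biopsies (section 4.1) may keep the non-measurable group small, and the low end of the table is then the relevant part.
- **Stakes.** The decision is whether to evaluate the combination further, in a 24-patient single-arm trial, and the biomarker comparison is exploratory.

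These points narrow the concern and lower its severity. None removes the conflict within section 10.5.2, and no other section supplies a threshold, a confirmation rule, independent review or separate reporting by measurability.

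**Conclusion.** The point holds. Section 10.5.2 sets RECIST 1.1 as the standard and then departs from it for non-measurable disease, with no confirmation. The bias in the response rate is direct. The bias in the clinical benefit rate is conditional: it needs a marker or pain response credited to a patient who does not reach 24 weeks without progression, and it needs the looser definition in sections 2.2 and 10.4.2 to be applied.

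On that reading and at a true rate of 10%, the false-go probability moves from 0.085 to between 0.096 and 0.414 over the assumed values, and to 0.193 with exactly one miscounted patient. These figures show sensitivity. They are not an estimate, because the documents give neither the non-measurable share nor a miscall rate. It would also go too far to conclude that the power calculation is wrong or that the primary rate is certainly inflated.

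This should be fixed, and settled before the primary analysis.

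**What to change.** 1. Replace the second paragraph of section 10.5.2.2. Class patients without measurable disease by the RECIST 1.1 imaging-based non-target categories (CR, non-CR/non-PD, PD), and apply to CR the same confirmation at 4 or more weeks.
2. Count clinical benefit in these patients only when the patient is progression-free (CR or non-CR/non-PD) through the scheduled 24-week assessment. Eight-weekly imaging falls at weeks 9, 17 and 25, so name the week-25 scan with its visit window. A strict cut-off at 24 weeks could exclude a scan taken slightly early but within the window.
3. Align sections 2.2, 10.4.2.1 and 10.4.2.2 with the synopsis endpoint at 24 weeks, and fill in the RECIST version in section 10.4.
4. Report the CR plus PR rate in patients with measurable disease at baseline. Report the clinical benefit rate overall and by measurability.
5. Report tumour markers and pain descriptively, outside response.

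The cost is mainly wording, and the change relies on imaging already scheduled. The response-rate denominator becomes smaller, and the clinical benefit rate may be lower. Patients whose only lesions are not shown on the scheduled CT, and who have no bone evaluation near week 24, would not count as clinical benefit; the plan should say so.

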10.5.2.3 Progression Free Survival

For all patients enrolled, PFS will be defined as the time from the first day of enzalutamide treatment (Study Day 1) until documented disease progression or death on study, whichever occurs first. For patients who do not die or experience disease progression on study, PFS will be right censored at the day of the last information available for progression assessment. Kaplan-Meier methods will be used to describe PFS by dose level and overall.

10.5.3 Receptor Expression

The degree of ER, PR, and AR expression in the nucleus will be reported by IHC strength of staining (0-3+) and % nuclei stained. The relationship between tumor response and degree of AR expression, and/or AR signaling, will be examined. Additional assays for AR signaling, (e.g., gene expression array analyses, mutation analyses, or other immunohistochemistry evaluations) may be performed on remaining tissue to evaluate for molecular phenotypes and patterns associated with activated AR signaling.

11. SOURCE DOCUMENTATION AND RETENTION OF RECORDS:

11.1 Data and CRFs

The clinical data will be collected on eCRFs and stored in a secure, encrypted RedCap file.

11.2 Data Accessibility and Record Keeping

The Investigator must make study data accessible to the Study Monitor or other authorized representatives of the Sponsor (or designee) and Regulatory Agency (e.g., FDA) inspectors upon request. A file for each patient must be maintained that includes the signed informed consent form and copies of all source documentation related to that patient. The Investigator must ensure the reliability and availability of source documents from which the information on the case report form was derived.

Investigators must maintain all study documentation for a period of 2 years following the approval date of the drug in breast cancer, or until 2 years after the investigational drug program is discontinued. Study documentation includes the Investigator's Brochure, signed protocol and amendments; signed informed consents; notifications of serious

adverse events and related reports; any dispensing and accountability logs; shipping records of investigational product and trial related materials; documentation of the financial aspects of the trial, insurance statement, and signed agreement between involved parties; dated and documented IRB approval, and approval of regulatory authority(ies); normal laboratory values; decoding procedures for blinded trials; initiation visit report; curricula vitae; and all correspondence pertaining to the conduct of the study. The Sponsor will notify the Study Investigator when any records may be discarded.

12. POTENTIAL SCIENTIFIC PROBLEMS:

12.1 Enzalutamide may not have sufficient anti-breast cancer activity in the clinic

Subsequent studies would then focus on defining the tumor characteristics that most likely would be sensitive to this or other AR signaling inhibitors and identifying rational combinations with enzalutamide to overcome this intrinsic resistance.

12.2 Inadequate collection of tissues and inadequate serial samples

We anticipate inadequate specimens in up to 10% of individuals. Each investigator is determined to collect these samples and is experienced in obtaining such specimens. Handling of these tissues is routine in all institutions. All participating sites are experienced NCI designated cancer centers, and have well developed phase I and breast cancer multidisciplinary programs. All sites see a large number of new breast cancer patients per year, and have high clinical trial accruals. All of the sites lead investigators are accomplished medical oncologists with experience with phase I/II and III trials. [name] in collaboration with [name], conducted the preoperative hormone trial that established the potential importance of AR and enzalutamide in ER+ breast cancer. University of Colorado has well-established core facilities to perform Nextgen sequencing, tissue banking and processing, and CLIA certified IHC.

12.3 Inadequate tissue biopsy samples in more than 10% of individuals

We would then consider increasing the patient enrollment to obtain 20 matched serial samples (pre-enzalutamide and after 4 weeks).

13. ETHICS:

The PI will ensure that this study is conducted in full conformity with regulations for the Protection of Human Subjects of Research codified in 45 CFR Part 46, 21 CFR Part 50, 21 CFR Part 56. ICH E6 may also be followed to the extent it has been adopted by and is in accordance with FDA regulations.

14. CONFLICT OF INTEREST:

Independence of this study from any actual or perceived influence, such as by the pharmaceutical industry, is critical. Any actual conflict of interest of persons who have a role in

the design, conduct, analysis, publication, or any aspect of this trial will be disclosed and managed by the University of Colorado Denver's (UCD) Office of Regulatory Compliance Conflict of Interest and Commitment Management (COIC) program. Persons with a perceived conflict of interest will have such conflicts managed in a way that is appropriate to their participation in the trial. Conflict of Interest management plans are project-specific and are reviewed at least annually. UCD has integrated the institutional conflict of interest management program with its existing program.

15. REFERENCES:

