1.4 Hypothesis

Enzalutamide with fulvestrant, by blocking both AR and ER signaling, will synergize in patients with ER+ AR+ metastatic breast cancer. It may prevent AR from taking over from ER when ER signaling is blocked. The extent of AR expression that correlates with enzalutamide efficacy is unknown and is an objective of this study; therefore, all patients, including those with “AR-negative” breast cancer (although this is expected to be fewer than 10%), will be enrolled to receive standard of care fulvestrant with enzalutamide. We hypothesize that 1) AR localization (a shift from nuclear to cytoplasmic) when comparing the pretreatment to the ~4 week tissues will represent a pharmacodynamics (PD) marker of enzalutamide activity. In tumors that respond to treatment, we would not only expect such a shift in AR localization, but also 2) a reduced expression in AR-regulated genes as well as subsequent changes in downstream processes. Thus, comparison of pre- vs during treatment tissues should allow us to identify PD markers as well as predictive biomarkers that indicate no response to enzalutamide (such as no

change in Ki67 or TUNEL). We will be able to measure Ki67 using standard IHC assays as well as a quantitative measurement by Reverse Phase Protein Microarray (RPMA). Multivariate analysis will be required to attempt to classify protein, gene, or TUNEL markers associated with PFS as predictive (of therapeutic impact), prognostic (of intrinsic tumor biology), or mixed as discussed above. A similar plan to compare the preclinical with the clinical analyses should facilitate the discovery and validation of putative biomarkers. The evaluation of Ki67 and TUNEL will provide the preliminary data necessary to mount our preoperative trial proposed in Years 3-5. Sample size and power consideration: 24 baseline samples will provide 80% power to detect a mean difference in change (baseline-during treatment) of 1 (or 1.3) standard deviation between the two groups (NR vs R) using one-sided 2-group t-test with a significance level of 0.05, assuming the response is 50% (or 20%). Statistical analysis plan: the same analysis approaches described in aim 1 will be used here, with the changes (baseline –during treatment) instead of the baseline values. Coefficient variation (CV) will be calculated for each potential biomarkers and biomarkers with smaller CV will be particularly interesting.

2. OBJECTIVES AND OUTCOMES:

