3.4 Sample Size

Twenty-four (24) evaluable patients will be recruited for this study. Up to 45 patients may be consented to allow for screen failures. The 24 evaluable patients will receive serial

tumor biopsies – pre-enzalutamide treatment and at ~4 weeks on therapy. Patients will be asked to allow an optional biopsy upon progression of disease.

4. STUDY ENROLLMENT AND WITHDRAWAL:

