10.2.2 Power Consideration

For the outcome lack of response, 24 samples gathered during years 1-2 provide 80% power to detect a minimum mean difference at baseline of 1.2 (or 1.5) standard deviation between the NR group vs all others (Response group, R), using a two-sided t-test with a significance level 0.5, assuming 50% (or 20%) response rate. Due to the exploratory nature of this aim, the type I error rate will not be adjusted for exploring multiple biomarkers.

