10.4 Research (Statistical) Methods

Data collected in this study will be presented using summary tables, patient data listings, and figures. Disease evaluations will be performed by investigators per the RECIST ___ criteria. Each enrolled patients will provide tumor tissues at baseline (0 week) and during treatment (4 weeks) and at disease progression. 24 pre- and treatment- biopsy pairs are planned for this study. Patients lacking pre- or treatment- biopsies will be replaced.

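### Sections 3.4 and 10.4 plan 24 biopsy pairs, but the contingency in 12.3 aims for only 20, is already satisfied when first triggered, and falls short of the 80% power stated in 1.4

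*Combined protocol and SAP*

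**What the plan says.** Section 3.4 sets the size of the trial: "Twenty-four (24) evaluable patients will be recruited for this study. Up to 45 patients may be consented to allow for screen failures". The evaluable patients are to have serial "tumor biopsies – pre-enzalutamide treatment and at ~4 weeks on therapy". Section 10.4 repeats the number and adds a replacement rule: "24 pre- and treatment- biopsy pairs are planned for this study. Patients lacking pre- or treatment- biopsies will be replaced".

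Section 12.2 allows for some loss: "We anticipate inadequate specimens in up to 10% of individuals". The next section, headed "12.3 Inadequate tissue biopsy samples in more than 10% of individuals", says what would happen beyond that: "We would then consider increasing the patient enrollment to obtain 20 matched serial samples (pre-enzalutamide and after 4 weeks".

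Two power statements rest on 24 samples. Section 1.4 covers the change from baseline to week 4: "24 baseline samples will provide 80% power to detect a mean difference in change (baseline-during treatment) of 1 (or 1.3) standard deviation", comparing non-responders with responders by a one-sided t-test at 0.05, with 50% (or 20%) response. Section 10.2.2 covers baseline values only: "24 samples gathered during years 1-2 provide 80% power to detect a minimum mean difference at baseline of 1.2 (or 1.5) standard deviation". No section gives power for 20 pairs.

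**The concern.** The plan carries two targets for matched tissue. In 10.4 the target is 24 and replacement is definite. In 12.3 it is 20 and extra enrolment is only to be considered. A plan to enrol more when samples fail should take effect when its trigger is met. This one appears not to, because its target lies below the number of pairs left at the trigger.

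Two things depend on this. One is how many patients are enrolled and biopsied after an unusable sample. The other is whether the 80% in 1.4 describes the tissue that will be collected. Two fresh biopsies are an eligibility condition (4.1), and serial biopsies are a secondary objective (2.3), so the number needed should be clear.

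**Working it through.** **1. When 12.3 takes effect.** Inputs: 24 planned pairs (3.4, 10.4), a trigger above 10% and a target of 20 (12.3). Assumption: the 10% is counted over 24 patients, since no denominator is given. Ten percent of 24 is 2.4, so the trigger is first met at 3 failures.

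| Inadequate | Share of 24 | Pairs left | Trigger met? | Below 20? |
|---|---|---|---|---|
| 2 | 8.3% | 22 | no | no |
| 3 | 12.5% | 21 | yes | no |
| 4 | 16.7% | 20 | yes | no |
| 5 | 20.8% | 19 | yes | yes |

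With 3 or 4 failures the trigger is met and the target is already reached. If the true failure rate were 10%, the top of the range in 12.2, the binomial chance of exactly 3 or 4 failures in 24 is 0.221 + 0.129 = 0.35.

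**2. Power for change (1.4).** For a two-group t-test with groups n1 and n2 and a difference of d standard deviations:

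- degrees of freedom = n1 + n2 − 2
- noncentrality δ = d × √(n1·n2/(n1 + n2))
- power = P(noncentral t > t(0.95, df)), one-sided 0.05

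The plan's own figure comes first, at 24 (20% of 24 is 4.8, taken as 5), then the figure for 20:

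| Pairs | Split | d | δ | Critical t | Power |
|---|---|---|---|---|---|
| 24 | 12/12 | 1.0 | 2.449 | 1.717 | 0.767 |
| 24 | 5/19 | 1.3 | 2.586 | 1.717 | 0.805 |
| 20 | 10/10 | 1.0 | 2.236 | 1.734 | 0.694 |
| 20 | 4/16 | 1.3 | 2.326 | 1.734 | 0.723 |

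The stated 80% is reproduced at 1.3 SD. At 1 SD it holds only roughly: the normal approximation, Φ(2.449 − 1.645), gives 0.789, and the exact t-test needs 1.05 SD. At 20 pairs the normal approximation gives 0.723 and 0.752, also below 80%. Solving power = 0.80 at 20 pairs gives δ = 2.585, so d = 2.585/√5 = 1.16 SD (10/10) and 2.585/√3.2 = 1.45 SD (4/16).

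**3. Baseline comparison (10.2.2).** This needs a usable baseline sample, not a pair. Taking the printed significance level of 0.5 as 0.05, the only reading that reproduces 80%, two-sided power at 24 is 0.802 (1.2 SD) and 0.814 (1.5 SD). It falls to 0.718 for both only if all four lost pairs lack a usable baseline sample. If the failures are at week 4, it does not change.

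**4. What replacement to 24 usable pairs does to the primary analysis.** At 10% inadequacy, 24/0.9 = 26.7, so about 27 treated patients. The efficacy population in 10.4.1 is everyone with at least 4 weeks of enzalutamide, so a patient whose week-4 core is unusable will usually remain in it. The decision table in 10.2.1 stops at 24. Exact binomial tails at 10% (alpha) and 30% (power):

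| n | R ≥ 5: alpha / power | R ≥ 6: alpha / power |
|---|---|---|
| 24 | 0.085 / 0.89 (as printed) | 0.028 / 0.77 |
| 25 | 0.098 / 0.91 | 0.033 / 0.81 |
| 26 | 0.112 / 0.93 | 0.040 / 0.84 |
| 27 | 0.127 / 0.94 | 0.047 / 0.86 |

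**The case against.** The two sections can be read together. Section 10.4 speaks of patients *lacking* a biopsy, and 12.3 of *inadequate* samples. On that reading the trial collects 24 pairs, expects some to be unusable, and treats 20 usable pairs as a floor. A reader might infer a flat contradiction between two binding rules. The documents do not support that: 12.3 is one tentative sentence in a chapter on potential problems, and it gives neither denominator nor timing. If the failure rate were watched during accrual, passing 10% could prompt a useful early review. This part of the objection stands. It leaves an unexplained difference in targets, and the documents never state the distinction that would reconcile them. Under it, 10.4 would also provide no replacement for an unusable core, so 12.3 would be the only rule for that case.

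A reader might also infer that 20 pairs undermine 10.2.2. That holds only for lost baseline samples. Nor is 20 alone to blame for missing 80%, since 24 pairs give 0.77 at 1 SD. The loss from 24 to 20 is about 7 points there and 8 at 1.3 SD, the latter partly from rounding 4.8 responders up to 5.

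The row for n = 20 in 10.2.1 might seem to justify 20 pairs. It does not: it concerns patients leaving before 24 weeks and the clinical benefit rate, not tissue.

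Finally, the tissue work is exploratory (synopsis endpoints, 10.2.2). That is right and limits the weight of the point.

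**Conclusion.** The point holds as a mismatch in the tissue target. The plan states 24 pairs in two places and 20 in a third without explanation. Counted over 24 patients, the contingency adds nobody until 5 have failed, about twice its stated threshold. At 20 pairs the change comparison in 1.4 has power of about 0.69 to 0.72, or 0.72 to 0.75 by normal approximation, against a stated 80%.

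This assumes the 10% is taken over 24, the splits are 10/10 and 4/16, and the t-test is as described in 1.4. It would be wrong to conclude that the trial's main result is weakened: the primary endpoint's stated power does not depend on 12.3. It should be corrected as a consistency matter in an exploratory aim.

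**What to change.** Use one target throughout. There are two ways.

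- **Keep 24.** In 12.3 change 20 to 24. In 10.4 extend replacement to biopsies that are *lacking or inadequate*. State that patients replaced only for tissue reasons stay in the clinical benefit analysis, and extend the decision table in 10.2.1 above n = 24. Keeping R ≥ 5 at n = 27 would raise alpha to 0.127; R ≥ 6 gives 0.047 with power 0.86. The cost is about 3 more treated patients at 10% inadequacy. This fits the limit of 45 consented only if screen failures allow, and no screen-failure rate is given.
- **Accept 20.** Say in 10.4 that 20 is the minimum number of usable pairs, and restate 1.4 for 20 pairs: 80% power for a difference in change of 1.16 SD (50% response) or 1.45 SD (20% response). The cost is a slightly less favourable detectable difference.

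Either way, give the denominator and timing of the 10% trigger in 12.3, and leave 10.2.2 based on the number of usable baseline samples.
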